11.7 Confidentiality of study documents and patient records

[figure not shown]
The investigator must ensure anonymity of the patients; patients must not be identified by names in any documents submitted to Novartis. Signed informed consent forms and patient enrollment log must be kept strictly confidential to enable patient identification at the site.

11.8 Audits and inspections

Source data/documents must be available to inspections by Novartis or designee or Health Authorities.

11.9 Financial disclosures

Financial disclosures should be provided by study personnel who are directly involved in the treatment or evaluation of patients at the site - prior to study start.

12 Protocol adherence

Investigators ascertain they will apply due diligence to avoid protocol deviations. Under no circumstances should the investigator contact Novartis or its agents, if any, monitoring the study to request approval of a protocol deviation, as no authorized deviations are permitted. If the investigator feels a protocol deviation would improve the conduct of the study this must be considered a protocol amendment, and unless such an amendment is agreed upon by Novartis and approved by the IRB/IEC/REB it cannot be implemented. All significant protocol deviations will be recorded and reported in the CSR.


The list of CYP inhibitors and inducers was compiled from the FDA's "Guidance for Industry, Drug Interaction Studies;" from the Indiana University School of Medicine's "Clinically Relevant" Table and from the University of Washington's Drug Interaction Database. Note that this may not be an exhaustive list. Please refer to footnotes.
 
¹ Effect seems to be due to CYP2C19 inhibition by ethinyl estradiol.
 
² Fluconazole is a dual CYP3A4 and CYP2C9 inhibitor. Fluconazole is a strong CYP2C9 inhibitor based on the AUC ratio of omeprazole, which is also metabolized by CYP3A; fluconazole is a moderate CYP3A inhibitor.
 
³ Herbal product.
 
⁴ Drugs not available in the US Market.
 
^a A strong inhibitor for a specific CYP is defined as an inhibitor that increases the AUC of a sensitive substrate for that CYP by equal or more than 5-fold.
 
^b A moderate inhibitor for a specific CYP is defined as an inhibitor that increases the AUC of a sensitive substrate for that CYP by less than 5-fold but equal to or more than 2-fold
 
^c A strong inducer for a specific CYP is defined as an inducer that decreases the AUC of a sensitive substrate for that CYP by equal or more than 80%.
 
^d A moderate inducer for a specific CYP is defined as an inducer that decreases the AUC of a substrate for that CYP by 50-80%.
	

Dual CYP2C9/CYP3A4 inhibitor:

Fluconazole: Avoid the concomitant use of ruxolitinib with fluconazole doses ≥ 200 mg daily; If clinically necessary to use doses ≥ 200 mg daily consultation with Sponsor is required. Please refer to [Section 6.4.2](#) (Permitted concomitant therapy requiring caution and/or action).

Appendix 2

Table 14-2 European Consensus on the grading of myelofibrosis (adapted from literature)

Grading	Description*
MF - 0	Scattered linear reticulin with no intersections (cross-overs) corresponding to normal bone marrow
MF - 1	Loose network of reticulin with many intersections, especially in perivascular areas
MF - 2	Diffuse and dense increase in reticulin with extensive intersections, occasionally with only focal bundles of collagen and/or focal osteosclerosis
MF - 3	Diffuse and dense increase in reticulin with extensive intersections with coarse bundles of collagen, often associated with significant osteosclerosis

*Fiber density should be assessed in hematopoietic (cellular) areas.

Adapted from: Thiele J et al. 2005; Haematologica ; 90:1128-1132 (European consensus on grading bone marrow fibrosis and assessment of cellularity).

Appendix 3

Table 14-3 Eastern Cooperative Oncology Group performance status

Grade	Performance Status
0	Fully active, able to carry on all pre-disease performance without restriction
1	Restricted in physically strenuous activity but ambulatory and able to carry out work of a light or sedentary nature, e.g., light house work, office work
2	Ambulatory and capable of all self-care but unable to carry out any work activities. Up and about more than 50% of waking hours
3	Capable of only limited self-care, confined to bed or chair more than 50% of waking hours
4	Completely disabled. Cannot carry on any self-care. Totally confined to bed or chair
5	Dead

Appendix 4

Patient reported outcomes – Questionnaires

MF-7 Myelofibrosis 7 Item Symptom Scale

Myelofibrosis 7 Item Symptom Scale (MF-7)	
Symptom	0 to 10 Ranking
Select the one number that describes the worst severity you have experienced with each of the following in the past 24 hours	
Tiredness	(Absent) 0 1 2 3 4 5 6 7 8 9 10 (Worst Imaginable)
Filling up quickly when you eat	(Absent) 0 1 2 3 4 5 6 7 8 9 10 (Worst Imaginable)
Abdominal discomfort	(Absent) 0 1 2 3 4 5 6 7 8 9 10 (Worst Imaginable)
Night Sweats	(Absent) 0 1 2 3 4 5 6 7 8 9 10 (Worst Imaginable)
Itching (pruritus)	(Absent) 0 1 2 3 4 5 6 7 8 9 10 (Worst Imaginable)
Bone pain (diffuse not joint pain or arthritis)	(Absent) 0 1 2 3 4 5 6 7 8 9 10 (Worst Imaginable)
Pain under ribs on left side	(Absent) 0 1 2 3 4 5 6 7 8 9 10 (Worst Imaginable)

EQ-5D-5L Health Questionnaire

EQ-5D-5L Health Questionnaire

Under each heading, please check the ONE box that best describes your health TODAY

MOBILITY

- I have no problems walking
- I have slight problems walking
- I have moderate problems walking
- I have severe problems walking
- I am unable to walk

SELF-CARE

- I have no problems washing or dressing myself
- I have slight problems washing or dressing myself
- I have moderate problems washing or dressing myself
- I have severe problems washing or dressing myself
- I am unable to wash or dress myself

USUAL ACTIVITIES

(e.g. work, study, housework, family or leisure activities)

- I have no problems doing my usual activities
- I have slight problems doing my usual activities
- I have moderate problems doing my usual activities
- I have severe problems doing my usual activities
- I am unable to do my usual activities

PAIN / DISCOMFORT

I have no pain or discomfort

I have slight pain or discomfort

I have moderate pain or discomfort

I have severe pain or discomfort

I have extreme pain or discomfort

ANXIETY / DEPRESSION

[figure not shown]
I am not anxious or depressed

I am slightly anxious or depressed

I am moderately anxious or depressed

I am severely anxious or depressed

I am extremely anxious or depressed

The best health you can imagine

100
95
90
85
80
75
70
65
60
55
50
45
40
35
30
25
20
15
10
5
0

The worst health you can imagine

- We would like to know how good or bad your health is TODAY.
- This scale is numbered from 0 to 100.
- 100 means the best health you can imagine. 0 means the worst health you can imagine.
- Mark an X on the scale to indicate how your health is TODAY.
- Now, please write the number you marked on the scale in the box below.

YOUR HEALTH TODAY =

USA (English) © 2009 EuroQol Group. EQ-5D™ is a trade mark of the EuroQol Group

**Document History – Changes compared to previous final version of SAP**

Date	Time point	Reason for update	Outcome for update	Section and title impacted (Current)
29-Jan-2016	Prior to DB lock	Creation of final version	N/A - First version	NA
19-Jul-2017	Prior to DB lock	Creation of amendment 1 due to study premature termination	Change to the ultimate goal of the early termination study: To present the efficacy, safety and [REDACTED] data of interest.	Introduction section 1.2
			Specified that primary endpoint PFS, and other time to event endpoints will not be derived.	Introduction section 1.2
			Removed Per-Protocol Set and PK Set, and Subgroup of interest.	Analysis sets Section 2.2
			Treatment period 1 data will be tabulated, Treatment period 1 and period 2 data will be listed.	Sections 2.3, 2.4, 2.5, 2.7, 2.8
			Specified that no analysis for primary endpoint is planned. The early terminated study aims to present data collected for the endpoints of interest, including change in spleen volume and length from baseline, change in symptoms using MF-7 and EQ-5D from baseline (see patient reported outcomes section), safety endpoints, [REDACTED]	Analysis of the primary objective section 2.5
			Descriptive statistics will be used to summarize the endpoints of interest and the FAS will be used for analyzing the data.	
			Specified that no sufficient data were collected to assess the effect of ruxolitinib versus placebo on overall survival and time to progression, so that no secondary	Analysis of the secondary objectives section 2.7

Date	Time point	Reason for update	Outcome for update	Section and title impacted (Current)
			efficacy analysis will be performed in this study.	
			AESI is not planned for this prematurely terminated study.	Section 2.8.1.1
			Add text to AE of clinical trial safety disclosure.	Section 2.8.1.2
			No formal PK analysis is planned. Individual plasma ruxolitinib concentration data will only be listed for the Full analysis set.	PK Section 2.9
				

## List of abbreviations

AE	Adverse event
ATC	Anatomical Therapeutic Classification
AUC	Area Under the Curve
bid	bis in diem/twice a day
CSR	Clinical Study Report
CTC	Common Toxicity Criteria
CTCAE	Common Terminology Criteria for Adverse Events
DMC	Data Monitoring Committee
FAS	Full Analysis Set
eCRF	Electronic Case Report Form
IRT	Interactive Response Technology that includes Interactive Voice Response System and Interactive Web Response System
MedDRA	Medical Dictionary for Drug Regulatory Affairs
NCI	National Cancer Institute
o.d.	Once Daily
OS	Overall Survival
PFS	Progression-Free Survival
PK	Pharmacokinetics
PPS	Per-Protocol Set
PRO	Patient-reported Outcomes
qd	Qua'que di'e / once a day
QoL	Quality of Life
RAP	Report and Analysis Process
RECIST	Response Evaluation Criteria in Solid Tumors
SAP	Statistical Analysis Plan
SOC	System Organ Class
TFLs	Tables, Figures, Listings
WHO	World Health Organization

## **1 Introduction**

The purpose of the Statistical Analysis Plan (SAP) is to describe the implementation of the statistical analysis planned in the protocol for the abbreviated clinical study report (CSR) and potential publications.

The study is terminated prematurely due to unresolvable recruitment issues. Descriptive statistics and listings of safety, efficacy and biomarker data of interest is planned for reporting CINC424A2353. No formal statistical analyses for progression free survival (PFS) are planned as the number of patients enrolled in the study is insufficient to perform confirmative analysis.

The latest MedDRA version by the time of DBL should be used for the CSR.

### **1.1 Study design**

This is a double blind, randomized placebo-controlled study of ruxolitinib in patients with HMR positive early MF (HMR+ EMF). The study consists of a screening period, Treatment Period 1 and Treatment Period 2.

Details of the discontinuation from study/treatment, unblinding, planning of the EOT assessment and safety monitoring are documented in the Premature Termination Plan.

#### **Screening:**

Patients will be pre-screened for the determination of HMR mutation status after obtaining the molecular pre-screening informed consent. Only patients who are centrally confirmed to be HMR+ will be eligible to enter the screening phase. Patients should be consented to the main study informed consent as soon as HMR positivity is confirmed (recommended within 28 days). Patients will be randomized in a 1:1 ratio to ruxolitinib or placebo on Day 1 following confirmation of eligibility, including confirmed bone marrow fibrosis grading during the 40 day screening period.

#### **Treatment Period 1**

[figure not shown]
Blinded study treatment will begin on Day 1 following randomization. Visits will be every 4 weeks up to Week 24 to monitor tolerability and efficacy with the study treatment. After Week 24, visits will be every 8 weeks until Week 48, and then every 12 weeks thereafter. Blinded study treatment will be administered until disease progression or patient discontinuation. A 30-day safety follow up visit will be done after the last dose of blinded study drug (except if entering Treatment Period 2). Patients who discontinue for reasons other than disease progression will enter the post treatment follow up. Patients will be followed for survival after end of Treatment Period 1 or post-treatment follow up every 3 months until the termination of study by the sponsor.

## Treatment Period 2

Patients who progress due to splenomegaly or symptoms and are candidates for treatment with currently approved doses of ruxolitinib (as per investigators decision) will be treated with ruxolitinib at 5mg, 15mg or 20 mg BID, based on platelet counts at the time of treatment initiation. These patients will continue on the same schedule of assessments as in ‘Treatment Period 1’. A 30-day safety follow up visit will be performed after the last dose of study drug. Patients will be followed for survival after end of Treatment Period 2 every 3 months until the termination of study by the sponsor ([Figure 1-1](#)).

[figure not shown]
### Figure 1-1 Schematic study design

#### A) Screening

## B) Treatment Period

## Randomization

Patients will be assigned to one of the two treatment arms in a ratio of 1:1 (ruxolitinib or placebo).

The randomization numbers will be generated using the following procedure to ensure that treatment assignment is unbiased and concealed from patients and investigator staff. A patient randomization list will be produced by the IRT provider using a validated system that automates the random assignment of patient numbers to randomization numbers. These randomization numbers are linked to the different treatment arms, which in turn are linked to medication numbers.

Prior to dosing, all patients who fulfill all inclusion/exclusion criteria will be randomized via IRT to one of the treatment arms. The investigator or his/her delegate will log on to the IRT and confirm that the patient fulfills all the inclusion/exclusion criteria. The IRT will assign a randomization number to the patient, which will be used to link the patient to a treatment arm and will specify a unique medication number for the first package of study treatment to be dispensed to the patient. The randomization number will not be communicated to the caller.

Randomization is not stratified.

## Interim analysis

The study is terminated prior to initial planned interim analysis due to unresolvable recruitment issue. Hence, one final analysis is planned for the abbreviated CSR and no interim analysis will be performed.

### 1.2 Study objectives and endpoints

Table 3-1 of CINC424A2353 study protocol specifies the study objectives and endpoints. The initial plan of efficacy evaluation and safety assessment of ruxolitinib cannot be implemented due to early termination of the study. The number of patients randomized and the study duration by termination were minimal and they did not provide sufficient information to perform formal comparison specified in the original analysis plan.

To present the efficacy, safety and [REDACTED] data of interest is the ultimate goal of the early termination study. The key endpoints of interest are listed in Table 1-1 below.

**Table 1-1 Endpoints of Interest**

Endpoint
Change in spleen volume (by MRI/CT) from baseline
Change in spleen size (by palpation) from baseline
Changes in symptoms using MF-7 and EQ-5D from baseline
The frequency, duration, and severity of adverse events including abnormalities in vital signs, laboratory parameters and ECG data
[REDACTED]
Plasma ruxolitinib concentrations
[REDACTED]
[REDACTED]

## 2 Statistical methods

This section contains information that will be used to draft CSR Section 9.7 on statistical analysis.

### 2.1 Data analysis general information

Data analysis for the clinical study report will be performed by Novartis personnel, Biostatistics and Statistical Programming department.. SAS version 9.4 or later will be used to produce statistical outputs. One final analysis will be performed for efficacy assessments and safety endpoints using data collected up to the cut-off date. The cut-off date is determined by the study termination date.

Only data with an assessment or event start date (e.g., vital sign assessment date or start date of an AE) prior to or on the cut-off date will be included in the analysis. For example: if cut-off date is 15-Jun-2014 then an AE starting on 13-Jun-2014 will be reported, whereas an AE with start date on 17-Jun-2014 will not be reported.

All events with start date before or on the cut-off date and end date after the cut-off date will be flagged as 'continuing at the cut-off date'. The same rule will be applied to events starting

before or on the cut-off date and not having documented end date. This approach applies, in particular, to adverse event and concomitant medication reports. For these events, the end date will not be imputed and therefore will not appear in the listings. However, for any analysis of duration of AE, the cut-off date will be used for censoring of this event which was ongoing at time of cut-off.

Data post cut-off will not be included in the analysis datasets and not listed.

All participating study centers will be combined for the analysis unless otherwise specified. In general, no center effect will be assessed due to expected small patient enrollment size of centers.

Since the randomization in this study is not stratified, no stratification factors are present.

**Categorical data** or qualitative characteristics of a subject (e.g., gender, race, subject disposition, etc.) will be summarized by frequency count (number of subjects) and percentages. Percentages will be calculated using the number of subjects in the relevant population or subgroup as the denominator.

**Continuous data** (e.g., age, body weight, etc.) will be summarized by appropriate descriptive statistics (mean, standard deviation, median, minimum, and maximum).

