8.1 Adverse events

8.1.1 Definitions and reporting

An adverse event is defined as the appearance of (or worsening of any pre-existing) undesirable sign(s), symptom(s), or medical condition(s) that occur after patient's signed informed consent has been obtained.

For patients who sign the molecular pre-screening ICF, AEs which occur after signature of this consent will only be captured if they meet the definition of serious as outlined in [Section 8.2](#) and are reported to be causally related with study procedures (e.g. an invasive procedure such as biopsy). Once the main study ICF is signed, all AEs per the descriptions below will be captured in the Adverse Event CRF.

Abnormal laboratory values or test results occurring after informed consent constitute adverse events only if they induce clinical signs or symptoms, are considered clinically significant, require therapy (e.g., hematologic abnormality that requires transfusion or hematological stem cell support), or require changes in study medication(s).

Adverse events that begin or worsen after informed consent should be recorded in the Adverse Events CRF. Conditions that were already present at the time of informed consent should be recorded in the Medical History page of the patient's CRF. Adverse event monitoring should be continued for at least 30 days following the last dose of study treatment. Adverse events (including lab abnormalities that constitute AEs) should be described using a diagnosis whenever possible, rather than individual underlying signs and symptoms. When a clear diagnosis cannot be identified, each sign or symptom should be reported as a separate Adverse Event.

Adverse events will be assessed according to the Common Terminology Criteria for Adverse Events (CTCAE) version 4.03.

If CTCAE grading does not exist for an adverse event, the severity of mild, moderate, severe, and life-threatening, corresponding to Grades 1 - 4, will be used. CTCAE Grade 5 (death) will not be used in this study; rather, information about deaths will be collected through a Death form.

The occurrence of adverse events should be sought by non-directive questioning of the patient (subject) during the screening process after signing informed consent and at each visit during the study. Adverse events also may be detected when they are volunteered by the patient (subject) during the screening process or between visits, or through physical examination,

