### 2.1.9 Last contact date

The last contact date will be derived for patients not known to have died at the analysis cut-off using the latest complete date among the following:

- Date of randomization
- Last contact date/last date patient was known to be alive from the Survival Follow-up page (if patients status is alive)
- Assessment dates (i.e. vital signs assessment, performance status assessment, and assessment date for spleen imaging, central laboratory, completed PROs)
- Start/end dates from drug administration records and for further antineoplastic therapies
- Adverse events dates including the start and stop date of AEs
- Date of discontinuation from ‘End of Treatment’ eCRF

The last contact date is defined as the latest complete date from the above list on or before the cut-off date. The cut-off date will not be used for last contact date, unless the patient was seen or contacted on that date. No date post cut-off date will be used.

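### SAP 2.1 flags and censors every open-ended AE at the study cut-off, with no exception for patients who died, withdrew or left AE follow-up before then

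*SAP*

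**What the plan says.** SAP 2.1 first flags events that start by the cut-off and end after it as continuing at the cut-off. It then extends the same treatment to events starting "before or on the cut-off date and not having documented end date". For all of these, "the end date will not be imputed and therefore will not appear in the listings". On duration it adds that "for any analysis of duration of AE, the cut-off date will be used for censoring of this event"; the sentence goes on to describe such an event as one still ongoing at the cut-off. The cut-off is common to all patients: "The cut-off date is determined by the study termination date".

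AE duration is in scope. SAP Table 1-1 lists as an endpoint of interest "The frequency, duration, and severity of adverse events including abnormalities in vital signs, laboratory parameters and ECG data". SAP 2.8 says that all safety data will be listed.

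The SAP also has a patient-level date. SAP 2.1.9 derives a last contact date for patients not known to have died, and states: "The cut-off date will not be used for last contact date, unless the patient was seen or contacted on that date". SAP 2.1 does not use that date, or any other patient-level date, for AE duration.

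**The concern.** A censoring time should be the last time at which the patient was known to be under observation with the event unresolved. A study-level cut-off meets that condition only for patients still in AE follow-up on that day. An AE that was open when a patient died, withdrew consent or was lost has no later information, yet SAP 2.1 carries it forward to the cut-off.

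Two outputs could be affected:

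- **Listings, which are planned.** An AE could be marked as continuing at cut-off in a patient who had died or left the study. That would be a factual error in the abbreviated clinical study report.
- **Any analysis of AE duration.** Unobserved time would be counted as time with the event unresolved, which overstates duration. SAP 1.2 describes the number of patients randomized as minimal, so a few such records could move a summary noticeably.

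**Working it through.** **Step 1. Does any provision cap the rule?**

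- SAP 2.1 names no exception for death, withdrawal or loss to follow-up.
- SAP 2.1.9 defines last contact but does not link it to AE duration.
- SAP 2.2.6 excludes data collected after full withdrawal of consent, but does not end an AE's duration there.
- SAP 5.1.2 gives imputation rules for AE onset date, causality and severity, and none for the end date.
- SAP 5.1.3.3 imputes partial death dates, but does not use them to close or censor AEs.

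No cap was found.

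**Step 2. Can an AE stay open after AE observation has ended?** Yes, by several routes in the protocol.

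- Withdrawal of consent (7.1.6): no further assessments, and no contact unless safety findings require it.
- Loss to follow-up (7.1.8): expressly provided for.
- Death from a cause other than the open AE.
- Survival follow-up (7.1.7.1): contacts collect survival, leukemic transformation and anti-neoplastic therapy. AEs are not listed.

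**Step 3. Size per event.** The documents give no figure to reproduce, and no AE, exit or cut-off dates. Let O be the onset day, L the last day AEs were assessed and C the cut-off. I count days inclusively, as SAP 2.4.1 does for exposure.

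- Duration under SAP 2.1 = C − O + 1
- Observed duration = L − O + 1
- Excess = C − L

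Assume O = 60. Each cell shows the SAP 2.1 duration, the observed duration and the excess, in days.

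| L | C = 180 | C = 365 | C = 540 |
|---|---|---|---|
| 90 | 121 / 31 / 90 | 306 / 31 / 275 | 481 / 31 / 450 |
| 120 | 121 / 61 / 60 | 306 / 61 / 245 | 481 / 61 / 420 |
| 180 | 121 / 121 / 0 | 306 / 121 / 185 | 481 / 121 / 360 |

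For example, with L = 90 and C = 365: 365 − 60 + 1 = 306, 90 − 60 + 1 = 31, and 365 − 90 = 275.

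**Step 4. Effect on a summary.** Assume ten AEs: eight resolved in 14 days, and two open with O = 60, L = 90 and C = 365.

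- Total time under SAP 2.1: 8 × 14 + 2 × 306 = 724 days. Mean recorded duration is 724/10 = 72.4 days. The exponential estimate (total time over resolved events) is 724/8 = 90.5 days.
- Total time censored at last AE assessment: 8 × 14 + 2 × 31 = 174 days. The mean is 174/10 = 17.4 days and the exponential estimate is 174/8 = 21.75 days.
- Kaplan-Meier: the proportion unresolved falls to 1 − 8/10 = 0.2 at Day 14 under both rules, so the median is 14 days either way.

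The effect therefore depends on the summary chosen, and the SAP names none.

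**The case against.** **No planned table uses the rule.** SAP 2.8.1 and 2.8.1.2 set out the AE summaries, and none reports duration. This stands, and it limits the practical effect. Table 1-1 still lists duration, SAP 2.1 legislates for any such analysis, and the flag appears in listings that are planned.

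**The censoring sentence covers only events ongoing at cut-off.** Read alone, it does. But the preceding sentences class every event without an end date as continuing at cut-off, so the qualifier excludes none of them.

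**A reader might infer that every patient who stops treatment is affected**, because Protocol 8.1.1 says "Adverse event monitoring should be continued for at least 30 days following the last dose of study treatment". The documents do not support that. Thirty days is a minimum. The same section requires AEs to be followed until resolution or until judged permanent. Protocol 6.3.2 requires continued follow-up, to resolution or stabilization, when an AE stopped treatment. Protocol 7.1.5 says that stopping treatment is not withdrawal from the study, and 7.1.7.2 provides continuing visits for patients without progression.

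**A reader might infer that SAP 2.1.9 prohibits the rule.** It does not, because it governs a different variable. It shows only that the SAP elsewhere declines to treat the cut-off as evidence that a patient was observed.

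**A reader might infer a bias between arms**, with longer durations in the arm with more early exits. That would need unequal exits with open AEs and a duration analysis. The documents establish neither.

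**Conclusion.** The point holds as a gap in SAP 2.1. For an AE open when a patient died, withdrew consent, was lost or otherwise left AE follow-up before cut-off, the flag is wrong. Any duration analysis would then include unobserved time equal to the cut-off minus the last AE assessment. In the assumed examples the excess runs from 0 to 450 days per event. It is always zero for patients followed to cut-off.

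The number of affected AEs and the true gaps cannot be found from the documents, and every date used in the working is an assumption. Discontinuing treatment does not by itself create the problem. The study ended early and reporting is descriptive, so no hypothesis test or primary result is touched. The correction is worth making because duration is a named endpoint and the listings will carry the flag.

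**What to change.** In SAP 2.1, censor an AE without an end date at the earliest of:

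- the cut-off date;
- the date of death;
- the date of consent withdrawal;
- the patient's last visit or contact at which AEs were assessed.

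The last item should not be replaced by the SAP 2.1.9 last contact date. That date can come from a survival-only contact, which does not collect AEs, so unobserved time would still be credited.

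Use 'continuing at the cut-off date' only for patients still under AE follow-up on that day. Otherwise use 'ongoing at death' or 'ongoing at last AE assessment'. In SAP 2.8.1, state whether AE duration will be summarised and by what method, so that Table 1-1 and the planned outputs agree.

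The cost is a short text change and one derived variable. Visit dates, the consent-withdrawal date (SAP 2.2.6) and death information (SAP 5.2) are already collected. The last AE-assessment date is not yet defined in the SAP and would be derived from the visit dates.
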